The study procedures outlined below cover 3 integrated experiments. A general overview of each study suggests a highly integrated set of experiments that will help explain neuromodulatory effects. **Study 1** investigates the effects of **frequency** and number of pulses, manipulated across blocks. rTMS is applied to MT or the vertex at 7 doses consisting of up to 30 pulses at 1, 5, or 10Hz. **Study 2** manipulates the **location** and orientation of the coil during rTMS of MT to bias rTMS effects either toward the dorsal pathway or toward the ventral pathway. **Study 3** manipulates **brain state** and uses *motion task blocks*, as in Studies 1 and 2, but also *color task blocks* and *rest blocks*. As in Study 2, only 5Hz rTMS is used. Therefore, we describe first the *shared* design information, and then describe design information *specific* to each of the 3 Studies.

Table 1. TIMELINE OF STUDY PROCEDURES:

Assessment	Screening Session	Session 1 (Shared)	Session 2 or 3 TMS-fMRI	Session 2 or 3 TMS-EEG
1. Subject consent & questionnaires	X			
2. Urine Test	X			
3. Practice with Motion task	X			
4. TMS Tolerability	X			
5. TMS Motion disruption, phosphene and motor thresholds	X			
6. Structural MRI (T1 & DWI)		X		
7. Resting-state fMRI		X		
8. Event-related fMRI with Motion task		X		
9. Concurrent TMS-fMRI with Motion task			X	
10. Concurrent TMS-EEG with Motion task				X
11. Side Effect Checklist	X		X	X

The Table above presents the timeline of major study procedures.

Shared Design Details

Subject Screening. In each of the 3 studies proposed, 48 different healthy young adults (18-30 y.o.) will participate in both TMS-MRI and TMS-EEG components of each study. Participants will have no psychiatric or neurological history and no ongoing psychoactive drug use (for more details see Section 5 below). Normal right-handed volunteers will be recruited from the community.

Each participant will take part in up to **seven** sessions: the first two sessions are *shared* by the TMS-MRI and TMS-EEG components of each study. The third and fourth sessions correspond separately to the TMS-fMRI and TMS-EEG sessions—with designs specific to each of the 3 Experiments—with the order counterbalanced across participants. If participants have been included in the pilot protocol, they will have two additional visits. Finally, an additional visit is built in if subjects need to make up a visit (e.g. poor task performance).

[figure not shown]

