Study 3 manipulates **brain state** and uses *motion task blocks*, as in Studies 1 and 2, but also *color task blocks* and *rest blocks* (Fig. 1B). As in Study 2, only 5Hz rTMS is used. Study 3 crosses stimulation site (rTMS to MT vs. vertex) and brain state (motion, color, rest). The color task starts like the motion task but, instead of moving, the dots change color. In both left and right circles, the dots are all grey during the stimulation period and turn blue or red during the “color period” (equivalent to the motion period). On the right side, 50% turn red and 50% blue, but on the left side, there is a greater proportion of blue or red dots. Subjects will press keys to report the more prevalent color. Difficulty is manipulated by varying the proportions of blue vs. red dots, which are titrated to match the difficulty of 3% vs. 18% motion coherence conditions. During rest blocks, participants rest while maintaining fixation.

Study 3 uses 6 conditions (Stimulation Site [vertex, target] x Brain State [color task, motion task, rest]) for rTMS stimulation. Each of the 6 conditions is assigned to three blocks of 20 trials each (60 trials/condition); each trial lasts 10 seconds, and we will administer 12 blocks (60 minutes, 360 trials total) in both the TMS-fMRI and TMS-EEG experiments. The TMS-fMRI and TMS-EEG will necessitate 60 minutes preparation to adjust the positioning for the TMS coil and—in the TMS—EEG experiment—apply the EEG cap, as well as 30 minutes for a brief rTMS side effect rating scale and visual analog mood ratings will be administered before and after each rTMS block. Thus, the entire session will last 3 hours for both the TMS-fMRI and TMS-EEG Session. As above, subjects' side effects will be monitored closely.

Piloting

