Piloting of the Motor Tasks and rTMS: In order to ensure success of the design proposed above, it will be critical to determine the proper timing of the rTMS effect. It is critical to determine the optimum stimulation onset to provide the maximal benefit to participants' working memory performance. As such, we plan to recruit 264 younger adults in an abbreviated version of the design for each Study presented above (88 participants per Study). Study procedures will be **identical** to those described above in **Table 1**, excluding Steps 6-10, which include MRI scanning. We will therefore rely on a non-MRI-based 10-20 system; while not as effective as fMRI-based targeting, using the 10-20 system for TMS positioning is applicable at low cost and may reach desired cortex regions reliably on a larger scale level (Herwig et al., 2003). Timing parameters for each piloting session are identical to those described above for **Study1/Study2/Study3**.

5. Selection of Subjects:

In each of the 3 studies proposed, 48 healthy young adults (18-30 y.o.) will participate in both TMS-MRI and TMS-EEG components of each study.

Study Inclusion Criteria:

1. Age restrictions
 - a. Age between 18-30.
2. Use of effective method of birth control for women of childbearing capacity.
3. Willing to provide informed consent.

Study Exclusion Criteria (ascertainment when appropriate):

1. Current or recent (within the past 6 months) of substance abuse or dependence, excluding nicotine and caffeine (urine test).
2. Current serious medical illness (self report).
3. History of seizure except those therapeutically induced by ECT (childhood febrile seizures are acceptable and these subjects may be included in the study), history of epilepsy in self or first degree relatives, stroke, brain surgery, head injury, cranial metal implants, known structural brain lesion, devices that may be affected by rTMS or MRI (pacemaker, medication pump, cochlear implant, implanted brain stimulator); [TMS Adult Safety Screening (TASS) form].
4. Subjects are unable or unwilling to give informed consent.
5. Diagnosed any Axis I DSM-IV disorder (MINI, DSM-IV)
6. Subjects with a clinically defined neurological disorder including, but not limited to:
 - a. Any condition likely to be associated with increased intracranial pressure
 - b. Space occupying brain lesion.
 - c. History of stroke.

- d. Transient ischemic attack within two years.
- e. Cerebral aneurysm.
- f. Dementia.

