- g. Mini Mental Status Exam (MMSE) score of <24.
- h. Parkinson's disease.
- i. Huntington's disease.
- i. Multiple sclerosis.
- 7. Increased risk of seizure for any reason, including prior diagnosis of increased intracranial pressure (such as after large infarctions or trauma), or currently taking medication that lowers the seizure threshold.
- 8. Subjects with cochlear implants
- 9. Subjects not willing to tolerate the confinement associated with being in the MRI scanner.
- 10. Women who are pregnant or breast-feeding (urine test).
- 11. Blindness.
- 12. Inability to read or understand English.

6. Subject Recruitment & Compensation:

We will recruit 264 total subjects into our 3 Studies. Prior to the main experiment for each Study, we will recruit pilot subjects to refine the experimental procedure and ensure adequate power (n=40 for each of 3 Studies, n=120 total). Then, for the main experiments, 48 subjects will be recruited for each study (n=144 total). Thus, 48 volunteers will be recruited for each Study, half male, half female, in order to achieve three groups of 38 completers for each study, given a 20% drop-out rate.

Subject Recruitment: Neurologically normal volunteers will be recruited from either a subject pool maintained at the BIAC for MRI (IRB protocol Pro00010672), [the](#) IBRC SONA site, Duke List (www.dukelist.edu), Craigslist, or flyers distributed on campus locations. Additionally, subjects who have participated in another active TMS Study (Protocol 000065334) and have explicitly indicated a willingness to be contacted for future experiments, may be contacted for participation in the current protocol. Male and female subjects from all racial and minority groups will be accepted.

Subject payment: \$20 per hour, approximately \$300.00 total for screening session (2 hrs), MRI session (2 hrs), and up to 4 additional sessions pairing TMS with another data collection technique (2 hrs each). 15 hours represents the maximum possible participation, including piloting and the full study, with the possibility of making up one visit. Payment will be made by via direct deposit for individuals with a Duke Unique ID or by check sent by mail within a few weeks after the end of their study involvement.

7. Consent Process:

Section 14 questions have been completed on the e-IRB submission form.

8. Subject's Capacity to Give Legally Effective Consent:

N/A: Only involves healthy volunteers

9. Study Interventions:

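### The pilot is 264 people in Section 4 but 120 in Section 6, and Study 3's stated 12 blocks should be 18 on its own figures

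*Combined protocol and SAP*

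**What the plan says.** **Pilot size.** Under Piloting, Section 4 states: "we plan to recruit 264 younger adults in an abbreviated version of the design for each Study presented above (88 participants per Study"). These people follow Table 1 without Steps 6-10, so they have no MRI, TMS-fMRI or TMS-EEG, and their coil is placed by the 10-20 system. Section 6 (Subject Recruitment & Compensation) opens with "We will recruit 264 total subjects into our 3 Studies". It then breaks that total into pilots, recruited partly to "ensure adequate power (n=40 for each of 3 Studies, n=120 total"), and the main experiments, where "48 subjects will be recruited for each study (n=144 total").

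**Overlap between pilot and main study.** Section 4 (Shared Design Details) says "If participants have been included in the pilot protocol, they will have two additional visits", and Section 6 says "15 hours represents the maximum possible participation, including piloting and the full study". Both allow one person to take part in both stages. Neither says how many may do so.

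**Study 3 blocks.** Section 4 (Study 3) says "Each of the 6 conditions is assigned to three blocks of 20 trials each (60 trials/condition") and, with 10-second trials, "we will administer 12 blocks (60 minutes, 360 trials total").

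**The concern.** The two sections give different pilot sizes in the current text. Section 4's 264 and 88 are exactly the figures that Section 6 builds from pilot plus main, which suggests that the overall total was entered as the pilot size. That origin is an inference; the conflict is not.

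In Study 3, the block count disagrees with every other figure in the same passage. Study 2 does have 12 blocks, so the number may have been carried over; that too is inferred.

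Both are figures that the trial acts on. The pilot size fixes how many healthy volunteers receive rTMS in piloting, and Section 13 asks a monitor to confirm that the plan is followed, which cannot be done against two values. The block count determines what is programmed for each session. The Piloting text makes pilot timing the same as in the corresponding Study, so a wrong count would carry into the Study 3 pilot as well.

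**Working it through.** **Inputs.** Section 4, Piloting: 264 pilots, 88 per Study. Section 6: 40 pilots and 48 main participants per Study, 264 overall, 38 completers, 20% drop-out. Section 4, Studies 1 to 3: conditions, blocks per condition, 20 trials per block, 10 s per trial.

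**Pilot and total**

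- Section 4 is consistent within its own sentence: 88 × 3 = 264.
- Section 6 pilot: 40 × 3 = 120. Main: 48 × 3 = 144. Total: 120 + 144 = 264, which reproduces Section 6.
- Per Study, pilot plus main: 40 + 48 = 88, the figure that Section 4 gives for the pilot alone.
- Difference in pilot size: 264 − 120 = 144, which equals 48 × 3.
- Main sample: 38 / (1 − 0.20) = 47.5, rounded up to 48; in reverse, 48 × 0.8 = 38.4. This reproduces.

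**Distinct people.** Let *k* be the number of pilots who continue into the main study. Distinct people = pilot + main − *k*.

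| Pilot size | *k* = 0 | Largest possible *k* |
|---|---|---|
| 120 | 120 + 144 = 264 | *k* = 120: 144 |
| 264 | 264 + 144 = 408 | *k* = 144: 264 |

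With 120 pilots, Section 6's 264 counts distinct people only if no pilot continues. With 264 pilots, it holds only if all 144 main participants are former pilots, and Section 6's pilot figure of 120 would still be wrong. The documents do not give *k*, so the table shows limits, not expectations.

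**Blocks.** Blocks = conditions × blocks per condition; trials = blocks × 20; minutes = trials × 10 / 60.

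| Study | Conditions × blocks | Blocks (stated) | Trials (stated) | Minutes (stated) |
|---|---|---|---|---|
| 1 | 7 × 2 | 14 (14) | 280 (280) | 46.7 (47) |
| 2 | 3 × 4 | 12 (12) | 240 (240) | 40 (40) |
| 3 | 6 × 3 | **18 (12)** | 360 (360) | 60 (60) |

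Studies 1 and 2 reproduce in full. In Study 3 only the block count fails.

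**If 12 blocks were run in Study 3:** 12 × 20 = 240 trials; 240 × 10 / 60 = 40 minutes; spread evenly, 240 / 6 = 40 trials per condition instead of 60. Study 3 gives 5 Hz but no train length. Assuming full 3-second trains, 5 × 3 = 15 pulses per trial, so a session would deliver 240 × 15 = 3,600 pulses instead of 360 × 15 = 5,400.

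**The case against.** The best defence is that these are slips the document largely resolves. Section 6 is the only place where 264 is built from its parts, so a careful reader would take 120 as the pilot size. In Study 3, all the other figures agree on 18, and the loss of trials occurs only if staff follow the one figure that is out of line. The main sample, endpoints and models do not change. All of that stands, and it limits the severity; it does not make the text right.

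Three readings that might rescue the wording fail:

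- *Section 4 means everyone, pilot and main.* It describes only people in the abbreviated design without Steps 6-10; main participants do have the MRI and EEG sessions.
- *Twelve counts task blocks only.* Two tasks × 2 sites × 3 blocks is indeed 12, but the sentence attaches 12 to 360 trials and 60 minutes, and rest is one of the six conditions.
- *Twelve blocks of 30 trials.* This gives 360 trials, but it contradicts 20 trials per block and three blocks per condition.

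A further objection is that 18 blocks may not fit the session. Preparation, task and ratings come to 60 + 60 + 30 = 150 minutes, within the stated 3 hours. Ratings are taken around each block, so the 30 minutes might have been set for 12 blocks; scaled up, 30 × 18 / 12 = 45 minutes, and the total is 165, still under 180. Section 6 does budget the TMS sessions at 2 hours each for payment. That conflicts with all three Studies (137, 130 and 150 minutes by the same sum), so it is a separate matter from the block count.

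**Conclusion.** Both contradictions hold. The pilot size is stated as 264 and as 120, a difference of 144 people that no amount of overlap removes. Study 3's stated 12 blocks should be 18 on its own conditions, blocks per condition, trials and minutes. The conflicts themselves need no assumption. The consequences are conditional: the distinct-participant limits depend on an overlap that is not stated, the drop from 60 to 40 trials per condition supposes that 12 blocks are run and shared evenly, and the pulse counts also assume 3-second trains. The point should be fixed because these are operating figures, but it does not bear on the validity of the main analyses.

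**What to change.** 1. **Section 4, Piloting:** change the pilot to 120 participants, 40 per Study. If 264 pilots are really intended, correct the pilot figure in Section 6 instead and restate the total of distinct participants, which would lie between 264 and 408.
2. **Overlap:** in either case, state how many pilots may continue into the main study, and whether 264 counts distinct people or enrolments.
3. **Section 4, Study 3:** change 12 blocks to 18.
4. **Optional wording, Section 6:** say one group of 38 completers in each of the three Studies.

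The cost is text corrections in one amendment. With 120 pilots there are no additional participants. With 18 blocks the task time stays at the stated 60 minutes and the session stays within 3 hours; the team should confirm that the 30-minute rating allowance was set for 18 blocks.

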2. *Motion period (3 s)*. The dots inside both circles start moving. All dots in the right circle move randomly in all directions (0% coherence—COH). Most dots in the left circle move randomly, but a percentage of dots move upward or downward together. The percentage of dots moving together is either high (18% coherence) or low (3% coherence) to make the task easy or hard (~90% or 60% correct, respectively, where chance=50%) as established in our pilot studies (Britten et al., 1992). Subjects indicate as quickly as possible whether the coherently moving dots in the left circle moved upwards or downwards through responses on two different buttons. Dot motion continues for 3 s regardless of response time. After the motion period, feedback for correct vs. incorrect responses is delivered: high- vs. low-pitch sounds (corresponding to high vs. low monetary payoffs at the end of the study).

3. *Inter-trial interval (ITI, mean: 4 s)*. Subjects maintain fixation on a central cross for a period varying between 2 and 7 sec (mean: 4 sec). This jittered ITI is critical for event-related fMRI analyses, but is also used to keep conditions identical.

Phosphene Threshold Determination: All rTMS procedures will occur in rooms 54210, 54211 and 54212 in the Department of Psychiatry and Behavioral Sciences, Duke Clinic South. Phosphene threshold is defined as the minimum magnetic flux needed to elicit phosphenes (the perception of moving lights in the absence of an actual visual stimulus) in 5 out of 10 trials. Like the motor threshold, phosphene threshold is a standard approach for determining the intensity of rTMS for each individual to reduce seizure risk. The phosphene threshold will be determined in a dark room using a blindfold to enhance the subject's ability to detect phosphenes. The presence of moving phosphenes will be identified by subject verbal response. The scalp region producing moving phosphenes will be identified and recorded on the BrainSight neuronavigation system. Phosphene and motion disruption threshold will be used to determine the exact location in V5 which is involved in motion perception; then intensity of stimulation over this specific area will be defined according to rMT. From this, we will confirm the target engagement.

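### The pilot places the coil by the 10-20 system for want of MRI, although a retained step already locates each participant's V5 site; the two passages must be reconciled

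*Combined protocol and SAP*

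**What the plan says.** Section 4, Piloting, makes the pilot procedures the same as those in Table 1, "excluding Steps 6-10, which include MRI scanning". From this it draws the placement rule: "We will therefore rely on a non-MRI-based 10-20 system; while not as effective as fMRI-based targeting". The support offered is that the 10-20 system is "applicable at low cost and may reach desired cortex regions reliably on a larger scale level".

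Table 1 lists as Step 5, in the screening session, "TMS Motion disruption, phosphene and motor thresholds". Being outside Steps 6 to 10, it remains in the pilot. Section 4, Phosphene Threshold Determination, describes what the step provides: "Phosphene and motion disruption threshold will be used to determine the exact location in V5 which is involved in motion perception". It adds: "The scalp region producing moving phosphenes will be identified and recorded on the BrainSight neuronavigation system".

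Section 6 gives the pilot's purpose: "we will recruit pilot subjects to refine the experimental procedure and ensure adequate power". Section 4, Piloting, gives it as finding the right timing and onset of stimulation. The pilot size is 40 per Study in Section 6 and 88 per Study in Section 4. The main studies are set at 48 recruited and 38 completers per Study. Their MT target comes from fMRI activation and E-field modelling (Section 4, Concurrent TMS-EEG Procedure).

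**The concern.** The piloting text treats the loss of MRI as leaving only scalp coordinates. Losing MRI removes fMRI-based targeting. It does not remove the individual functional site that, on the protocol's own account, is found at screening before any scan. The plan has a measured target for a participant and then names a generic one for positioning, without saying how the two relate. Two operators could place the coil differently on the same person and both be following the protocol.

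At stake is what the pilot can show. Choosing an onset, refining the procedure and judging whether power is adequate all need a visible rTMS effect at MT. If the coil is off target in some participants, the average effect shrinks. A null or small result could then mean wrong timing, no effect or wrong place, and the pilot data could not separate these.

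**Working it through.** **Step 1. Which steps stay.** Table 1 has 11 steps. Removing Steps 6 to 10 leaves Steps 1 to 5 and Step 11, so Step 5 is in the pilot.

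**Step 2. Does the inference follow?** The premise is that there is no MRI. The conclusion is 10-20 placement. It would follow only if MRI were the sole source of an individual target. The Phosphene Threshold Determination text names another source, and Table 1 puts it in the screening session, ahead of the MRI session. The conclusion does not follow.

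**Step 3. The plan's own figures.** Section 12, Study 1, says 30 per group suffices for a medium effect at alpha 0.05, without stating power. Assume a paired contrast, d = 0.5, two-sided 5% and 80% power. The normal formula gives n = (1.96 + 0.8416)² / 0.5² = 31.4, so 32. The exact paired t test gives 34, with 75% power at 30. The stated 30 is therefore roughly reproduced, which makes d = 0.5 a reasonable anchor. For dropout, 38 / 0.80 = 47.5, so 48, as stated. Power at 38 completers is 85%.

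**Step 4. Illustrative loss in the pilot.** All placement inputs are assumptions:
- Placement error is two-dimensional Gaussian with per-axis SD s of 5, 8 or 10 mm.
- rTMS has its full effect within radius r of MT (10 or 15 mm) and none beyond.
- The true paired effect is 0.5 with unit SD.
- The undiluted comparison assumes perfect placement.

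Formulas:
- Hit rate: h = 1 − exp(−r² / 2s²).
- Observed effect, with the hit/miss variance included: d′ = 0.5h / √(1 + 0.25h(1 − h)).
- Power: noncentral t on n − 1 degrees of freedom with noncentrality d′√n.

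Example with r = 10 and s = 8: h = 1 − exp(−100/128) = 0.542. The mean effect is 0.271, the SD is √(1 + 0.25 × 0.542 × 0.458) = 1.031, and d′ = 0.263. At n = 40 the noncentrality is 0.263 × √40 = 1.66 and power is 37%.

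| r (mm) | s (mm) | Hit rate | d′ | Power, n = 40 | Power, n = 88 | n for 80% power |
|---|---|---|---|---|---|---|
| no error | – | 100% | 0.50 | 87% | 99.6% | 34 |
| 10 | 5 | 86% | 0.43 | 75% | 98% | 46 |
| 10 | 8 | 54% | 0.26 | 37% | 68% | 116 |
| 10 | 10 | 39% | 0.19 | 22% | 43% | 217 |
| 15 | 5 | 99% | 0.49 | 86% | 99.6% | 35 |
| 15 | 8 | 83% | 0.41 | 71% | 96.5% | 50 |
| 15 | 10 | 68% | 0.33 | 53% | 86% | 75 |

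**Step 5. Direction for sizing.** If a diluted effect c × 0.5 were used to set N, the required N would grow roughly as 1/c². At c = 0.8 it goes from 34 to 52 completers. The error is towards a larger main study or a false alarm about power.

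**The case against.** The strongest reply is that the plan does not say the Step 5 site is discarded. The coil could be placed by 10-20 and the position then refined or confirmed with Step 5. The phosphene text does end by speaking of confirming target engagement, and the piloting sentence compares 10-20 only with fMRI-based targeting. That reading is possible, but the positioning sentence does not state it, so the need to reconcile the two places stands.

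Several further points stand in full:
- The documents rank 10-20 below fMRI-based targeting. They do not rank it against phosphene or motion-disruption mapping, and they give no yield or precision for that mapping.
- The Session 1 text describes these thresholds as serving dosing. The phosphene text, however, assigns them to location and ties intensity over that area to the resting motor threshold.
- Dilution that is the same at every onset costs precision but does not change which onset is best.
- The harsher figures depend on n = 40 and the 10-mm radius. At the 88 per Study in the piloting text, the loss is much smaller over most of the range.

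A reader might infer that pilot stimulation does miss MT in part. The documents do not show this: they concede lower effectiveness and give no miss rate. A reader might also infer that a diluted pilot effect will set the sample size and leave the main studies underpowered. No text converts a pilot effect into N. The main N is already fixed at 48 recruited per Study, the power statement rests on a generic medium effect and earlier working-memory studies, and dilution would push N up.

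**Conclusion.** The point holds as an inconsistency with a practical consequence. The piloting text rests 10-20 placement on the absence of MRI, while the protocol says a retained, MRI-free step locates the individual V5 site. As written, a generic coordinate is used where an individual functional site is already available. This can weaken the MT effect and make a null or small pilot result hard to interpret, whether the question is timing, procedure or power.

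The size of the loss cannot be computed from the documents. Under the stated assumptions, pilot power is about 22% to 86% at 40 per Study, against 87% undiluted, and about 43% to 99.6% at 88 per Study, against 99.6%. The range therefore runs from negligible to severe. It depends on the assumed placement error, the all-or-none radius, d = 0.5 and a comparison that gives perfect placement to the alternative, so it is an upper bound on what Step 5 targeting could recover. The risk is a misleading pilot.

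**What to change.** In Section 4, Piloting, for the Study 1 and Study 3 pilots:
- Position the MT coil at the participant's own Step 5 site as recorded on neuronavigation.
- Use the 10-20 coordinate only when Step 5 yields no site, and flag those participants.
- Analyse all pilot participants together, with a sensitivity analysis by targeting method. Do not restrict decisions to those with a Step 5 site, because that selects participants in a way the main studies do not.
- Leave the intensity rules as they are.

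The Study 2 pilot is outside this change, because its dorsal and ventral conditions are built from fMRI, tractography and E-field models that the pilot lacks.

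The cost is a sentence or two of text and a targeting flag in the data. No visit, scan or procedure is added, since Step 5 is already done. The downsides are that some participants will have no Step 5 site, so targeting will be mixed, and that Step 5 targeting still does not fully match the fMRI and E-field targeting of the main studies. Pilot effect sizes should be reported with that caveat.

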Study 1 investigates the effects of **frequency** and number of pulses, manipulated across blocks. Table 2 describes the 7 conditions used in this experiment. rTMS is applied to MT or the vertex at 7 doses consisting of up to 30 pulses at 1, 5, or 10Hz. In conditions 1–3, these frequencies are delivered for 3 seconds leading to 3, 15, and 30 pulses, respectively. In conditions 4 and 5, frequency remains at 10Hz, but durations are 1.5 and .3 seconds, respectively, to yield

Table 2. Conditions in Study 1

Cond	Sites	Hz	Sec.	Pulses
1	MT	1	3.0	3
2	MT	5	3.0	15
3	MT	10	3.0	30
4	MT	10	1.5	15
5	MT	10	0.3	3
6	Vtx	1	3.0	3
7	Vtx	10	3.0	30

numbers of pulses that match conditions 1 and 2. Thus, we manipulate frequency while keeping duration constant, and number of pulses while keeping frequency constant. In control vertex stimulation conditions 6 and 7, rTMS is delivered for 3 seconds at 1Hz or 10Hz, matching the pulses of conditions 1 and 3, respectively.

Each of the 7 conditions is assigned to two blocks of 20 trials each (40 trials/condition); each trial lasts 10 seconds, and we will administer 14 blocks (47 minutes, 280 trials total) in both the TMS-fMRI and TMS-EEG experiments. The TMS-fMRI and TMS-EEG will necessitate 60 minutes preparation to adjust the positioning for the TMS coil and—in the TMS—EEG experiment—apply the EEG cap, as well as 30 minutes for a brief rTMS side effect rating scale and visual analog mood ratings will be administered before and after each rTMS block. Thus, the entire session will last 3 hours for both the TMS-fMRI and TMS-EEG Session. As above, subjects' side effects will be monitored closely, and all side effect monitoring described above will be repeated. Furthermore, all intensities fall within the rTMS safety guidelines (Rossi et al., 2009b).

Study 2

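### Section 6 lists the TMS sessions at 2 hours where Section 4 gives 3, so the stated maximum of 15 hours and about $300 is not supported

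*Combined protocol and SAP*

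**What the plan says.** Section 6, Subject payment, sets a rate of $20 per hour and an overall figure of about $300. It counts 2 hours each for the screening and MRI visits. The other visits it lists are "up to 4 additional sessions pairing TMS with another data collection technique (2 hrs each". It then states that "15 hours represents the maximum possible participation, including piloting and the full study, with the possibility of making up one visit".

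Section 4 gives a different length for the TMS sessions. After itemising preparation, task and rating time, the text for each of Studies 1, 2 and 3 ends the same way: "Thus, the entire session will last 3 hours for both the TMS-fMRI and TMS-EEG Session".

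On the number of visits, Section 4 (Subject Screening) says "Each participant will take part in up to seven sessions". Two are shared (screening and MRI) and two are the TMS-fMRI and TMS-EEG sessions. For the rest, "If participants have been included in the pilot protocol, they will have two additional visits", and "an additional visit is built in if subjects need to make up a visit". Section 4 gives no length for the make-up visit. Its Piloting paragraph says that the timing parameters match those of the main studies, but it also calls the design abbreviated and leaves out the MRI, TMS-fMRI and TMS-EEG steps. No total length for a pilot visit is given.

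**The concern.** TMS-fMRI and TMS-EEG are the sessions that pair TMS with another technique, so the two sections give different lengths for the same visits. Section 6 uses its shorter length to describe what a volunteer will be asked to give and what they will be paid. Section 10 says that participants gain nothing beyond compensation and the goodwill of helping research, so hours and payment matter to them. If the TMS session length is wrong in Section 6, the burden is understated for every main-study participant, and the 15-hour maximum may be too low for those who also pilot.

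**Working it through.** **Inputs**

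- Rate: $20 per hour (Section 6).
- Screening visit: 2 h (Section 6; Section 4 gives no total for this visit).
- MRI visit: 2 h (Sections 4 and 6 agree).
- TMS-fMRI and TMS-EEG sessions: 2 h each in Section 6, 3 h each in Section 4.
- Pilot visits: two, total length not stated. Call it p hours.
- Make-up visit: one, length not stated. Call it m hours.
- Session components (Section 4): 60 min preparation, 30 min ratings, 10 s per trial, and 280, 240 and 360 trials in Studies 1, 2 and 3.

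**Step 1. Section 6's own figures.** The payment step reproduces: 15 × $20 = $300. The hours do not follow from the listed lengths. The six listed visits give 2 + 2 + 4 × 2 = 12 h. The stated maximum also includes a make-up visit:

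- 2-h make-up: 12 + 2 = 14 h
- 3-h make-up: 12 + 3 = 15 h

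So 15 h appears only if the make-up visit takes 3 h, a length that Section 6 uses for no visit.

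**Step 2. Does a TMS session fit in 2 hours?** Content = 60 + (trials × 10 / 60) + 30 minutes.

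| Study | Task (min) | Total (min) | Over 120 min by |
|---|---|---|---|
| 1 | 280 × 10 / 60 = 46.7 | 136.7 | 16.7 |
| 2 | 240 × 10 / 60 = 40 | 130 | 10 |
| 3 | 360 × 10 / 60 = 60 | 150 | 30 |

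Study 3 gives both 360 trials and 12 blocks. Twelve blocks of 20 trials would be 240 trials, or 40 min of task, and the session would still need 130 min. On either reading, no study's itemised content fits in 2 hours.

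**Step 3. Main-study participant, no pilot and no make-up.**

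- Section 6 lengths: 2 + 2 + 2 × 2 = 8 h, × $20 = $160
- Section 4 lengths: 2 + 2 + 2 × 3 = 10 h, × $20 = $200

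The difference is 2 h and $40.

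**Step 4. Participant who uses all seven visits, with 3-h main TMS sessions.** Hours = 2 + 2 + 2 × 3 + 2p + m = 10 + 2p + m.

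| Pilot visit p (assumed) | Make-up m = 2 h | Make-up m = 3 h |
|---|---|---|
| 1 h | 14 h, $280 | 15 h, $300 |
| 1.5 h | 15 h, $300 | 16 h, $320 |
| 2 h | 16 h, $320 | 17 h, $340 |
| 3 h | 18 h, $360 | 19 h, $380 |

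**Step 5. When does 15 h hold?** Setting 10 + 2p + m ≤ 15 gives p ≤ (5 − m) / 2. That is p ≤ 1 h with a 3-h make-up and p ≤ 1.5 h with a 2-h make-up. If the pilot visits are among Section 6's four additional 2-h sessions, p = 2 and the total is 16 to 17 h.

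**The case against.** The strongest reply is that Section 6 is a payment paragraph and not a schedule. Section 4 governs procedures and says 3 hours three times. Pay is by the hour, the $300 is approximate and no payment cap is stated, so actual pay may follow actual time. That limits the harm, but it does not reconcile 2 hours with 3, and the 15 hours, unlike the $300, is worded as a maximum.

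The reply is also right that the ceiling matters only to people who pilot. Without piloting, the most anyone gives is 2 + 2 + 3 × 3 = 13 h. With 2-h pilot visits and no make-up, the total is 14 h. If all five TMS visits ran only for the itemised minutes, the totals would be 4 + 5 × 130/60 = 14.8 h (Study 2), 4 + 5 × 136.7/60 = 15.4 h (Study 1) and 4 + 5 × 150/60 = 16.5 h (Study 3). Those lie near 15 h, but they set aside the 3 hours that the plan itself states.

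A reader might infer more than the documents support:

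- **That the sections disagree on the number of visits.** They do not. Section 6's screening, MRI and four further sessions, plus the make-up visit, come to the seven in Section 4.
- **That Section 6 adds to 12 hours and not 15.** The 12 hours leaves out the make-up visit, which the stated maximum includes. The like-for-like figure is 14 h, or 15 h with a 3-h make-up.
- **That trials or post-stimulation ratings would be lost.** Nothing suggests that staff would book sessions from the payment paragraph.
- **That volunteers have been misinformed at consent.** The consent pages are not in the text available for review, so this cannot be judged.

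**Conclusion.** The point holds, and its core needs no assumption: the same TMS sessions are 2 hours in Section 6 and 3 hours in Section 4, and their itemised content of 130 to 150 minutes exceeds 2 hours in every study. Taking the 2-hour screening visit from Section 6, the effect for a main-study-only participant is 10 h and $200 against 8 h and $160.

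The 15-hour maximum is unsupported, but how far it is exceeded depends on lengths that the plan does not give. With pilot visits assumed to take 2 h, the seven-visit total is 16 to 17 h. The 19 h ($380) is an upper bound that needs 3-h pilot and make-up visits, and it should not be read as the plan's own figure. The abbreviated pilot design leaves room for shorter visits, and at about 1 to 1.5 h the total returns to 15 h. How many participants would use all seven visits is not stated.

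No endpoint, analysis or safety rule changes. The figures are worth correcting because they describe participant burden and compensation, and the correction is cheap.

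**What to change.** Reconcile the TMS session length in Section 6 with Section 4. State the lengths of the pilot visits and the make-up visit. Then restate the maximum hours and the matching payment by adding up those lengths at the existing rate of $20 per hour.

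This is a wording amendment. If every TMS, pilot and make-up visit is set at 3 hours, the maximum becomes 19 h and $380, which is 4 h and $80 above the present statement ($380 − $300). That is the most it could add per participant relative to the stated maximum; shorter pilot or make-up visits would add less.
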